4.2 Exclusion Criteria

Patients who have any of the following diagnoses or conditions will be excluded from participating:

- cardiovascular disease, previous myocardial infarction, stent, CABG, arrhythmia, high or low blood pressure;
- recurrent stomach upset, or gastric or duodenal ulcers;
- gallstones or gall bladder disease (cholelithiasis);
- liver or kidney disease; high alcohol use (more than two drinks per day on a regular basis);
- Coumadin or anti-platelet drug use;
- at risk for respiratory depression, history of seizures, or taking drugs that reduce the seizure threshold or may increase the risk for development of serotonin syndrome;
- pregnant or breast feeding, or intention to become pregnant during the study;
- pronounced allergies, or known allergy to *H. procumbens* or corn starch;
- have had an injection to treat OA within the past three months;
- currently taking NSAIDs, unless they are willing to stop for a 1-week wash-out period;
- currently on a SSRI but are poorly stabilized, or have evidence of suicidal ideation and/or suicide attempts in the past year; and,

- reported use during the 7 days prior to study drug administration of: prescription medicines, or over-the-counter medications; non-steroidal anti-inflammatory medications (e.g., NSAIDs); dietary supplements; grapefruit and/or its juice products; or products containing St. John's Wort.

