6. STUDY PROCEDURES

6.1 Schedule of Evaluations

Assessment	Screening: Visit (2 – 14 days Before Testing Session)	PK Testing Session – Visit 1 (Time 0)	Follow-up - Visit 2 (24 hr)	Follow- up: Phone Contact (36 hr)
Informed Consent Form	X			
Demographics	X			
Medical History	X			
Current Medications	X	X		
Vital Signs	X	X	X	
General Physical Examination	X			
Electrocardiogram (ECG)	X		X	
Laboratory Values (CBC, CMP, LFT)	X		X	
Randomization		X		
Receive Daily Dose of Study Product		X		
Study Product Markers		X	X	
Measures of Side Effects		X	X	
Report of Adverse Events		X	X	X
Patient Reimbursement	\$50	\$125	\$50	

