6.2 Description of Evaluations

6.2.1 Screening Evaluation

The Screening Evaluation session to determine whether the patient is eligible to participate in the PK Study will occur from 2 to 14 days before the PK testing session. The Screening session will include the informed consent procedure and screening activities to ensure eligibility (described below).

Consenting Procedure

Prior to participants' participation in the study, written informed consent for the study, including screening and study procedures, will be obtained from each participant. CRC project staff or [name] will ensure that the participant is given full and adequate oral and written information about the nature, purpose, possible risk and benefit of the study. The participant's signed and dated informed consent will be obtained before conducting any study specific procedures. The CRC will store the original, signed Participant Informed Consent Form and a copy will be given to the participant.

Screening

Only volunteers who consent and pass all screening assessments will be scheduled for a PK testing session. Study participation will begin within 14 days of the Screening Evaluation session. At the screening session, the individual's SID number will be used to label all study data collected at the Screening session.

Following the completion of the informed consent procedures during the Screening session, a brief survey will be completed before other screening procedures are conducted. The survey will include items to record demographic information needed to describe the study sample (e.g., age, gender, race and ethnicity) and items to record contact information (e.g., address, phone number / email address).

The following eligibility screening evaluations will be completed.

- Medical history interview – Medical history will be collected via interviews. Participants will be asked about all previous diagnoses, allergies, procedures, and treatments to verify relevant inclusion/exclusion criteria (Section 4).
- Current medication use – Participants will provide a listing of all medications (prescription and over-the-counter) they are currently taking.. Anyone who reports using medications listed in Section 4.2 Exclusion Criteria will be asked to stop use of the product for 14 days before the PK testing session.
- Vital signs – The following vital signs will be recorded to verify they are within normal ranges: heart rate, blood pressure, respiration rate.

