- General physical examination – A general physical examination will be conducted.
- Electrocardiogram (ECG) – Standard 12-lead ECGs will be performed at the Screening and 24-hour follow-up sessions. The site study physician will review

the recording and verify that the participant has a normal ECG.

- Laboratory values – Blood samples will be obtained for CBC, BMP, LFT and HCG (pregnancy) for baseline product marker assays. The study physician will review the CBC, BMP, LFT and HCG (pregnancy) results to verify eligibility.

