6.2.2 Enrollment, PK testing, and/or Randomization

Enrollment

Participants who are judged to be eligible to participate by the study physician following all screening procedures will be contacted and scheduled for the PK testing session. At the testing session, participants will be assigned a participant identification number (PID). This PID is linked to their blinded randomization assignment, and linked to their SID.

PK Testing

During the PK testing session (Visit 1) the following assessments will be obtained.

- Current medication use – Participants will provide a listing of any and all medications (prescription and over-the-counter) they have taken since the Screening Session. Anyone who reports using any product listed in Section 4.2 Exclusion Criteria will have the PK testing session rescheduled to allow for a 7-day washout period during which they do not take any of the restricted medications.
- Vital signs – The following vital signs will be recorded as baseline values: heart rate, blood pressure, respiration rate.
- Study product markers – Blood samples will be obtained in order to assess product markers at timed intervals during the 10-hour testing session. Using an indwelling catheter that is inserted in the arm, two samples of blood will be collected at the following intervals following dosing: 0hr, 1 hr, 2 hr, 3 hr, 4 hr, 5 hr, 6 hr, 8 hr, 10 hr. This data collection timing schedule is based on previous research.¹

An exploratory examination of the presence of study product markers in urine will be conducted by collecting random urine samples that are timed, to the extent possible, to blood collection time points. Examination of study product markers in urine is exploratory, and will be conducted with the goal of further informing our understanding of the PK parameters obtained from blood samples. Samples for the measurement of study product markers will be analyzed under the supervision of [name].

- Side effects – Study staff will record occurrence of any side effects during the PK testing session.
- Adverse Events – Any occurrence of an adverse event noted by study staff or reported by a participant will be recorded and categorized by system.

Following all testing session assessments, the appointment time for the follow-up session will be confirmed and the participant will be paid for the testing session.

Randomization

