Random assignment into study group will occur upon arrival at the PK testing session. Participants will be assigned to one of two study groups – enteric capsules or non-enteric capsules.

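### Pregnancy is an exclusion, but the only pregnancy test is at screening, 2 to 14 days before the dose; Visit 1 lists no repeat, and the 6.1 schedule omits HCG

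*Protocol*

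**What the plan says.** Section 4.2 excludes anyone who is "pregnant or breast feeding, or intention to become pregnant during the study". Section 4.1 admits adults from 18 years with no upper age limit and no restriction to women who cannot conceive. The Précis plans six women among the 12 participants.

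Section 6.2.1 includes HCG among the screening blood tests and states its use: "The study physician will review the CBC, BMP, LFT and HCG (pregnancy) results to verify eligibility". The screening session "will occur from 2 to 14 days before the PK testing session", and the same section adds: "Study participation will begin within 14 days of the Screening Evaluation session".

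For Visit 1, section 6.2.2 lists current medications, vital signs, product markers, side effects and adverse events. On allocation it says: "Random assignment into study group will occur upon arrival at the PK testing session". The dose follows at the same visit.

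In the 6.1 table the laboratory row begins "Laboratory Values (CBC, CMP, LFT" and is marked at Screening and at the 24-hour visit. No row or column mentions HCG. Section 7.2 likewise places the laboratory safety measures at screening and 24 hours.

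**The concern.** The protocol relies on its eligibility criteria to keep people with a contraindication away from the extract (5.1, 7.2). It also accepts that eligibility can change between screening and dosing. A participant who reports a restricted product at Visit 1 "will have the PK testing session rescheduled to allow for a 7-day washout period". Pregnancy status can change, or first become detectable, over the same interval, yet nothing comparable is listed for it. Excluding women who intend to become pregnant does not cover an unintended pregnancy.

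What is at stake is participant safety and adherence to the protocol's own exclusion. The pharmacokinetic analysis is not at stake. Separately, staff who work from the 6.1 table alone could miss the one pregnancy test that the text does order.

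**Working it through.** The protocol gives no figure to reproduce. The check sets the sections side by side and then sizes the gap.

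**Step 1: where pregnancy is checked.**

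| Point in the study | Medications | Pregnancy test |
|---|---|---|
| Screening (6.2.1) | Yes | Blood HCG |
| Screening column of the 6.1 table | Yes | Not shown |
| Visit 1, before randomization and dose (6.2.2) | Yes, with rescheduling if needed | None listed |
| Visit 2, 24 hours (6.2.4) | Not listed | None listed |

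The visible text has no later pregnancy test and no contraception requirement.

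**Step 2: size of the gap.**

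Inputs:
- Gap g from screening test to dose: 2 to 14 days (6.1, 6.2.1).
- Lag from conception to a positive HCG: 10 to 14 days, with urine never earlier than blood. This is an assumption; the protocol gives no value. Write Lb for the blood lag and Lu for the urine lag.

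Formulas, for the span of conception dates before dosing that stays undetected:
- Screening test only: g + Lb
- With a Visit 1 urine test added: min(g + Lb, Lu)
- Gain: the difference, which is max(0, g + Lb − Lu)

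Results in days:

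| g | Lb | Lu | Screening only | With Visit 1 test | Gain |
|---|---|---|---|---|---|
| 2 | 10 | 10 | 12 | 10 | 2 |
| 2 | 14 | 14 | 16 | 14 | 2 |
| 2 | 10 | 14 | 12 | 12 | 0 |
| 14 | 10 | 10 | 24 | 10 | 14 |
| 14 | 14 | 14 | 28 | 14 | 14 |
| 14 | 10 | 14 | 24 | 14 | 10 |

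With equal lags the gain equals the gap. In the least favourable case (Lb = 10, Lu = 14) the gain is max(0, g − 4): nothing at gaps of 2 to 4 days, 1 day at a gap of 5, and 10 days at a gap of 14. These are days of undetected window, not probabilities of harm.

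**The case against.** The strongest reply is that this is a coherent design choice. The protocol excludes pregnancy and the intention to become pregnant, orders a blood test, has a physician review it and limits the interval to 14 days. Nothing in the document requires a dosing-day repeat, so only the table omission is a plain inconsistency. That is fair as far as it goes, and it keeps the point at low severity. It does not explain why medications are rechecked on the day and pregnancy is not.

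A reader might infer that nothing at all between screening and dose could bring a pregnancy to light. The document does not support that. Section 7.4 has the investigator ask about adverse events at every visit, and 4.2 still applies to a woman who discloses a pregnancy at Visit 1. The removed consent pages may also carry instructions to participants. However, the inquiry does not name pregnancy and is not tied to a decision before dosing, so it does not replace a test.

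A reader might also infer that a repeat test would close the gap. It would not: very early pregnancies stay undetectable, and at short gaps the test may add nothing. This stands as a limit on the benefit.

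Nor does the table omission mean that no pregnancy test is planned, since 6.2.1 orders one.

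**Conclusion.** The point holds at low severity. The protocol's only pregnancy test is 2 to 14 days old when the dose is given, Visit 1 lists no repeat before randomization and dosing, and the 6.1 table leaves HCG out.

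Under the assumed lag of 10 to 14 days, a Visit 1 test would shorten the undetected window by 0 to 2 days at a 2-day gap and by 10 to 14 days at a 14-day gap. The lag is the only outside assumption, and the textual finding does not depend on it.

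The absolute risk is small: a single dose and six planned women, of whom an unknown number, possibly none, could conceive. The documents describe no specific reproductive hazard of the extract, and none should be inferred. Sample size, endpoints and analysis are unaffected. The reason to act is that a safety exclusion can be rechecked on the dosing day at almost no cost.

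**What to change.** 1. In 6.2.2, add a urine HCG on arrival at Visit 1 for women of childbearing potential, and require a negative result before randomization and dosing. State that this applies equally to a rescheduled Visit 1. Testing before allocation matters: a positive result after allocation would leave a randomized participant who cannot be dosed.
2. In 6.1, list HCG in the Screening and Visit 1 columns so that the table agrees with the text.

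The cost is one urine test and a few minutes for those of the six planned women who could conceive, at a visit that already collects urine, plus two table entries. The limitation is that the test shortens the undetected window without closing it, and may add little when screening was only a few days earlier.

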6.2.2 Enrollment, PK testing, and/or Randomization

Enrollment

Participants who are judged to be eligible to participate by the study physician following all screening procedures will be contacted and scheduled for the PK testing session. At the testing session, participants will be assigned a participant identification number (PID). This PID is linked to their blinded randomization assignment, and linked to their SID.

PK Testing

During the PK testing session (Visit 1) the following assessments will be obtained.

- Current medication use – Participants will provide a listing of any and all medications (prescription and over-the-counter) they have taken since the Screening Session. Anyone who reports using any product listed in Section 4.2 Exclusion Criteria will have the PK testing session rescheduled to allow for a 7-day washout period during which they do not take any of the restricted medications.
- Vital signs – The following vital signs will be recorded as baseline values: heart rate, blood pressure, respiration rate.
- Study product markers – Blood samples will be obtained in order to assess product markers at timed intervals during the 10-hour testing session. Using an indwelling catheter that is inserted in the arm, two samples of blood will be collected at the following intervals following dosing: 0hr, 1 hr, 2 hr, 3 hr, 4 hr, 5 hr, 6 hr, 8 hr, 10 hr. This data collection timing schedule is based on previous research.¹

An exploratory examination of the presence of study product markers in urine will be conducted by collecting random urine samples that are timed, to the extent possible, to blood collection time points. Examination of study product markers in urine is exploratory, and will be conducted with the goal of further informing our understanding of the PK parameters obtained from blood samples. Samples for the measurement of study product markers will be analyzed under the supervision of [name].

- Side effects – Study staff will record occurrence of any side effects during the PK testing session.
- Adverse Events – Any occurrence of an adverse event noted by study staff or reported by a participant will be recorded and categorized by system.

Following all testing session assessments, the appointment time for the follow-up session will be confirmed and the participant will be paid for the testing session.

Randomization

Random assignment into study group will occur upon arrival at the PK testing session. Participants will be assigned to one of two study groups – enteric capsules or non-enteric capsules.

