5. STUDY INTERVENTIONS

5.1 Interventions, Administration, and Duration

The intervention to be tested in this study is oral doses of HP extract packaged in capsules prepared under GMP with extract containing approximately 25mg of harpagoside, without or with enteric coating. Comparison of enteric and non-enteric formulations is warranted by reports the anti-inflammatory and analgesic activity of HP extracts, and purified harpagoside, are sensitive to gastric acid.²⁸⁻³⁰ A dose will consist of sufficient capsules to achieve consumption of 100mg harpagoside daily.

H. procumbens supplements are widely used in Europe and are widely-available in the United States in grocery stores, health food stores, and pharmacies. Previous research using dose levels in the range of 50-100mg harpagoside daily dose has shown it to be at least as well tolerated as more traditional pain medication (e.g., nonsteroidal anti-inflammatory drugs)^{8,9} and allergies have been rare.

Screening criteria address any possible risks by excluding people with conditions that might be contraindicated. We will monitor possible side effects and adverse events during the PK testing session and at each post PK testing session contact. In addition, participants will be given a phone number to contact study staff and/or the investigators to report side effects or adverse events that occur following the testing session. Any problems needing medical attention will immediately be triaged by [name] and when appropriate, referred to the participant's personal physician or other health care providers. Diagnostic laboratory tests will be ordered as specified by the study physician.

Potential side effects of *H. procumbens* supplements include mild gastrointestinal symptoms such as diarrhea, nausea, vomiting, abdominal pain; headaches; ringing in the ears; loss of appetite; and, loss of taste. It may also be related to allergic skin reactions, menstrual problems, and changes in blood pressure.⁴¹ These were reported in less than 10% of people who took it in previous research; no serious adverse events were reported.³ These side effects may be treated with an appropriate medication determined by [name] or the subject's personal physician.

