6.2.4 Follow-up Evaluations

24 hr Evaluation

The following measurements and procedures will be completed at the 24-hour follow-up session.

Visit 2 (24 hours following dosing during the PK Testing Session):

- Vital signs – The following vital signs will be recorded: heart rate, blood pressure, respiration rate.
- Electrocardiogram (ECG) – Standard 12-lead ECGs will be performed at the 24-hour follow-up session. A study physician will review the recording and interpret the findings.
- Laboratory values (CBC, BMP, LFT) – Blood samples will be obtained and CBC, BMP, and LFT assays will be assayed. [name] will review and interpret the lab results.
- Study product markers – Blood and urine samples will be obtained in order to assess level of product markers.
- Side effects – Study staff will record any side effects reported by the participant.
- Adverse Events – Any occurrence of an adverse event reported by a participant will be recorded and categorized by system (i.e., cardiovascular, dermatologic, endocrine/metabolic, gastrointestinal, hematologic, hepatic, musculoskeletal, neurologic, renal, reproductive, or respiratory).

36 hr Follow-up. A phone contact will be made at 36 hours following the dosing time at the PK testing session (i.e., 24 hours following the end of the testing session). During this contact, information regarding any side effects or adverse events that were experienced since the last study visit will be collected.

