7.1 Specification of Safety Parameters

Safety and potential toxicity of HP extract ingestion will be evaluated by measuring vital signs; capturing adverse events; and, screening for potential renal, hepatic, metabolic, muscle, cardiac and hematological toxicity (by measuring biochemical and hematological parameters and by recording electrocardiograms (ECG)). Based on previous research and standard practice regarding monitoring the use of NSAIDs, CBC, BMP, and LFT assay results will be evaluated as primary safety measures. Examples of parameters that will be indicative of safety concerns include: a clinically meaningful drop in hemoglobin which could indicate GI bleeding; clinically meaningful changes in creatinine; and, clinically meaningful changes in liver function test parameters.

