7.2 Methods and Timing for Assessing, Recording, and Analyzing Safety Parameters

H. procumbens (Devil's Claw) is a widely-prescribed product in Europe and is widely-available in the United States in grocery stores, health food stores, and pharmacies. Numerous reviews provide a summary of safety-related information.^{3,10,34-41} Previous research using dose levels in the range of 50-100mg harpagoside daily dose has shown it to be at least as well tolerated as more traditional pain medication (e.g., nonsteroidal anti-inflammatory drugs),^{8,9} and allergies have been rare. Potential side effects of *H. procumbens* (Devil's Claw) include mild gastrointestinal symptoms such as diarrhea, nausea, vomiting, abdominal pain; headaches; ringing in the ears; loss of appetite; and, loss of taste. It may also be related to allergic skin reactions, menstrual problems, and changes in blood pressure.⁴¹

Screening criteria address possible risks by excluding people with conditions that might be contraindicated. We will monitor possible side effects and adverse events during the testing session and at each follow-up contact, and participants will be given a phone number to contact study staff and/or the investigators to report side effects or adverse events, if needed. Any problems needing medical attention will immediately be triaged by [name] and when appropriate, referred to the participant's personal physician or other appropriate health care providers.

Laboratory-based safety measures and the ECG will be assessed at the screening session to determine eligibility and at the 24-hour follow-up session (Visit 2) to assess health status following dosing. Vital signs will be collected at each study visit. Self-reported adverse events and side effects will be recorded at the follow-up sessions, and participants will be instructed to contact a member of the study team at any time during participation to report an adverse event.

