9.2 Sample Size and Randomization

Sample size is based upon previous research published by Loew and colleagues¹ in which six healthy adult males received a single 150mg harpagoside dose through consumption of 600mg *Harpagophytum* extract HF 8858. The C_{max} value was reached within 1.3 hours following dosing and was calculated as 32.2 ng/mL; the half-life of this dose level was 5.6 hours. Given our plan to compare pharmacokinetic parameters between participants who are dosed with enteric versus non-enteric coated capsules, we doubled the sample size used by Loew and colleagues in order to do this comparison. We will collect complete data from 12 participants.

Treatment Assignment Procedures

Group assignment will be linked to the participant identification (PID) number that will be assigned at the start of the PK Testing Session. Study staff responsible for the PK Testing Session will be given the appropriate PID number to use for the participant attending the Testing Session; the PID number will not indicate specifics of the study product assigned to the individual.

All study staff who have direct contact with study participants and/or are involved in data collection or analysis, including the PI and the study biostatistician, will be blinded as to randomization assignment into study group (i.e., enteric or non-enteric capsules). Knowledge of random assignment will remain blinded until all preliminary data reviews and quality checks are completed.

The randomization procedures and assignment list will be the responsibility of [name], DSMB member. She will have no direct involvement with the study participants, data collection, or statistical analysis of the study data.

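### No vital sign or ECG is scheduled between dosing and 24 h, although blood pressure change is a listed possible effect and safety is to be judged partly on these measures

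*Protocol*

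**What the plan says.** On possible effects of the product, section 5.1 of the Protocol states: "It may also be related to allergic skin reactions, menstrual problems, and changes in blood pressure". Section 7.2 repeats this. Section 7.1 says safety will be evaluated through vital signs, adverse events, laboratory tests and ECGs, the last two as part of "screening for potential renal, hepatic, metabolic, muscle, cardiac and hematological toxicity".

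The timing of vital signs and ECGs is set as follows:

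- Screening (6.2.1), 2 to 14 days before dosing: "The following vital signs will be recorded to verify they are within normal ranges: heart rate, blood pressure, respiration rate".
- Visit 1, the dosing session (6.2.2): "The following vital signs will be recorded as baseline values: heart rate, blood pressure, respiration rate".
- Visit 2 (6.2.4), headed "Visit 2 (24 hours following dosing during the PK Testing Session": vital signs, ECG and safety laboratory tests.
- ECG (6.2.1): "Standard 12-lead ECGs will be performed at the Screening and 24-hour follow-up sessions".
- General rule (7.2): "Vital signs will be collected at each study visit". It gives no times within a visit.

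During the 10 h session, blood for product markers is drawn through a catheter at 0, 1, 2, 3, 4, 5, 6, 8 and 10 h. Staff also record side effects and adverse events during the session.

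**The concern.** The only post-dose vital signs and the only post-dose ECG come a full day after a single dose. The protocol's own reference study puts the harpagoside peak at 1.3 h, when the participant is still in the research centre with staff at hand. A blood pressure change that came and went during the session without symptoms would leave no trace in the data. Section 7.1 relies on vital signs for the safety evaluation, and blood pressure is the one vital sign that the protocol itself ties to the product. For that effect, the schedule samples before exposure and near the end of it, but not in between.

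**Working it through.** **Where the readings fall.** The wording in 6.2.2 settles the Visit 1 reading, because it calls the values baseline. The Time 0 heading in the 6.1 table is weaker evidence: the same column carries the marker draws and side-effect recording, which run through the session, so it labels the visit rather than one clock time. The general rule in 7.2 is met by one reading per visit and does not add a post-dose reading at Visit 1.

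**Inputs.** Sections 2.2 and 9.2 give a peak reached within 1.3 h, and state that "the half-life of this dose level was 5.6 hours". Both figures come from six healthy men given 150 mg harpagoside in extract HF 8858. This study gives 100 mg in its own extract.

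**Share of peak remaining at time t**, taking 1.3 h as the peak and assuming log-linear decline:

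f(t) = 2^(−(t − t_max)/t_half)

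- Time from peak to the 24 h reading: 24 − 1.3 = 22.7 h, and 22.7/5.6 = 4.05 half-lives.
- f(24) = 2^(−4.05) = 0.060, about 6%.
- Check with a one-compartment oral model, C(t) ∝ e^(−kt) − e^(−ka·t), with k = ln 2/5.6 and ka = 2.41 per hour solved to give a 1.3 h peak: C(24)/C(1.3) = 0.063.

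**Sensitivity.** The protocol gives none of these alternative values; they are assumptions.

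- Enteric coat delays the peak by 3 h: 2^(−(24 − 4.3)/5.6) = 0.087.
- Enteric coat delays the peak by 6 h: 2^(−(24 − 7.3)/5.6) = 0.127.
- Half-life 4 h, no delay: 2^(−22.7/4) = 0.020.
- Half-life 8 h, no delay: 2^(−22.7/8) = 0.140.

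**Schedule against expected exposure** (no delay, half-life 5.6 h):

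| Time | Vital signs | ECG | Share of peak |
|---|---|---|---|
| Screening | yes | yes | none (before dosing) |
| Visit 1 baseline | yes | no | none |
| 2 h draw | no | no | 92% |
| 4 h draw | no | no | 72% |
| 6 h draw | no | no | 56% |
| 10 h draw | no | no | 34% |
| Visit 2, 24 h | yes | yes | 6% |

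The 1 h draw comes before the reference peak, so the formula does not apply to it. With a 3 to 6 h delay the peak would fall at 4.3 to 7.3 h, still inside the session.

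**The case against.** The case against is substantial, and several stronger readings fail.

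**Contradiction.** A reader might infer that the sections conflict. They do not. Sections 6.1, 6.2.1, 6.2.2, 6.2.4 and 7.2 give one consistent schedule, and 7.1 names the tools without promising a reading near the peak. The issue is how well the timing serves the stated purpose.

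**Nothing measured at peak.** This is also too strong. Product markers are drawn at eight post-dose times, and staff record side effects and adverse events throughout the session. The gap is confined to vital signs, ECG and safety laboratory tests.

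**Cardiac toxicity as a second product risk.** Section 7.1 mentions it within a general organ screen. The side-effect lists in 5.1 and 7.2 contain no cardiac or rhythm effect. Blood pressure is the only listed effect that bears on this point.

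**Misreporting.** A reader might expect a normal 24 h reading to be reported as proof of no effect. The protocol states no such claim; its outcomes are pharmacokinetic and it has no secondary outcomes.

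**Low stakes.** The study gives a single dose, at a level the protocol regards as safe. It excludes people with cardiovascular disease, arrhythmia or high or low blood pressure, and requires a normal ECG at entry. It reports side effects in fewer than 10% of earlier users, with no serious events, and names blood counts, metabolic panel and liver tests as the primary safety measures. All of this stands and limits the consequence.

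**No link from plasma level to blood pressure.** This also stands. The protocol does not say that any pressure effect follows harpagoside concentration. The one in vivo effect it reports, a fall in cysteinyl-leukotrienes, is at 8 h. Yet 8 h also lies inside the interval with no vital signs, so a later effect of that kind would be missed as well.

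**Conclusion.** The point holds in a limited form. No vital sign or ECG is scheduled between dosing and 24 h, and the 24 h reading comes about four half-lives after the reference peak, with about 6% of peak harpagoside expected. Across the assumed ranges (half-life 4 to 8 h without delay, or an enteric delay of 3 to 6 h at the reference half-life) the share is 2% to 14%. The absence of readings is plain from the text. The percentages are indicative only, since they rest on a different extract and dose in six healthy men, and the protocol gives no kinetics for the enteric capsule or the other markers. The consequence is that an asymptomatic, transient blood pressure change would go unrecorded. The documents do not support reading this as an internal contradiction, a failure to monitor participants during the session, or evidence that the product has a cardiac risk.

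**What to change.** Align the measurement times in 6.1, 6.2.2 and 7.2 with the safety purpose in 5.1 and 7.1. Record the vital signs already listed (heart rate, blood pressure, respiration rate) at some of the post-dose draws already scheduled in the session. Include early and late draws, so that a delayed enteric peak is also covered, and leave the choice of times to the investigators. Show the added times in the 6.1 table and on the CRF.

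In 7.1, state that the 24 h ECG cannot speak to effects around peak exposure. If no in-session vital signs are added, say the same of the 24 h vital signs.

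The cost is a protocol and CRF edit, a few minutes of staff time at draws where staff are already with the participant, and a few more fields to enter. No extra visit or blood is needed. This concerns only when measurements are taken and what they can show; no rule for clinical action is proposed.
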